Study Device:	
The COVERA™ Vascular Covered Stent is a highly flexible self-expanding endoprosthesis comprised of expanded polytetrafluoroethylene (ePTFE) encapsulating a nitinol (nickel-titanium alloy) stent framework. The inner lumen of the stent graft (blood contacting surface) is carbon impregnated.
 
The COVERA™ Vascular Covered Stent is available in a straight and a flared configuration. Devices will come on either an 8F or 9F system.
 
Table 1: COVERA™ Vascular Covered Stent Sizes
 
  
 Covered Stent Outer Diameter (mm)	Covered Stent Length (mm)	Endovascular System Length (cm)	
 
 30*	40	60	80	100	
   
 6	✓	✓	✓	✓	✓	80 and 120	
 
 7	✓	✓	✓	✓	✓	
 
 8	✓	✓	✓	✓	✓	
 
 9	✓	✓	✓	✓	✓	
 
 10	✓	✓	✓	✓	✓	
  
 
* Note: only the straight configuration of the implant is available in 30mm length.
	Covered Stent Outer Diameter (mm)	Covered Stent Length (mm)					Endovascular System Length (cm)	30*	40	60	80	100	6	✓	✓	✓	✓	✓	80 and 120	7	✓	✓	✓	✓	✓	8	✓	✓	✓	✓	✓	9	✓	✓	✓	✓	✓	10	✓	✓	✓	✓	✓
Covered Stent Outer Diameter (mm)	Covered Stent Length (mm)					Endovascular System Length (cm)																																						
	30*	40	60	80	100																																							
6	✓	✓	✓	✓	✓	80 and 120																																						
7	✓	✓	✓	✓	✓																																							
8	✓	✓	✓	✓	✓																																							
9	✓	✓	✓	✓	✓																																							
10	✓	✓	✓	✓	✓																																							
Enrollment:	Enrollment will continue until a total of one-hundred nine (109) subjects are treated with the COVERA™ Vascular Covered Stent. All subjects will be followed for 24 months post index procedure.																																											
Investigational Sites:	Up to 30 investigational sites in the United States (US).																																											

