2.2 Analysis populations

The analysis populations will be defined as follows for this study:

- The ITT population will consist of all subjects that have met all eligibility criteria, undergone successful PTA of the target lesion, and into which the COVERA™ Vascular Covered Stent System is introduced (i.e. the delivery system enters the subject's body).

Subjects who do not receive the study device, but into which the COVERA™ Vascular Covered Stent System was introduced, will be included in the ITT population. Subjects who require additional treatment modalities will be included in the ITT population.

- The Modified ITT (MITT) population will consist of any subjects in the ITT population who are treated with the COVERA™ Vascular Covered Stent (following PTA).
- A Per-Protocol (PP) population may be created if there are subjects who have any major protocol deviations. The PP population will consist of any subjects in the MITT population who do not have any major protocol deviation. The protocol deviations that are considered to have a "major" grade will be defined a priori in the analysis plan.

All analyses including the primary analyses will be primarily based on the MITT population. Key safety analysis will be performed based on ITT population as well. PP analyses may also be performed for the primary endpoints. They will only serve as sensitivity analyses for the primary analyses which are based on the MITT population.

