2.6.2 Primary Effectiveness Endpoint Hypothesis Test

The primary effectiveness endpoint is TLPP through 6-months. Objective: To assess if the 6 month TLPP for the COVERA™ Vascular Covered Stent is greater than the effectiveness PG.

The primary effectiveness endpoint will be evaluated by the following hypothesis:

H₀: The proportion of subjects in the study device treatment group (P_{CE}) with TLPP through 6 month post index procedure is less than or equal to that of the effectiveness PG of 40%.

H₁: The proportion of subjects in the study device treatment group (P_{CE}) with TLPP through 6 month post index procedure is greater than that of the effectiveness PG of 40%.

That is:

H₀: $P_{CE} \leq 40\%$,

H₁: $P_{CE} > 40\%$,

Rejection of the null hypothesis will signify that the 6 month TLPP of the COVERA™ Vascular Covered Stent is greater than the effectiveness PG of 40%.

A one sided p-value will be derived based on an exact binomial test. The study device will be considered to have achieved the primary effectiveness objective if the one-sided p-value is less than 0.05. Or equivalently, the lower limit of the one-sided 95% confidence limit based on exact method is greater than 40%.

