2.7 Evaluation of Secondary Endpoints

The following secondary endpoints will be summarized with descriptive statistics (without formal statistical hypothesis testing) using the MITT population. For categorical variables, summary statistics will include frequency counts and percentages. For continuous variables, summary statistics will include mean, standard deviation, minimum, median, and maximum.

- TLPP through 30 days, 90 days, 12 months, 18 months, and 24 months.
- ACPP through 30 days, 90 days, 6 months, 12 months, 18 months, and 24 months.
- Rate of device and procedure related AEs involving the AV access circuit through 90 days, 6 months, 12 months, 18 months, and 24 months.

- Total Number of AV Access Circuit Reinterventions through 30 days, 90 days, 6 months, 12 months, 18 months, and 24 months.
- Total Number of Target Lesion Reinterventions through 30 days, 90 days, 6 months, 12 months, 18 months, and 24 months.
- IPF evaluated at 30 days, 90 days, 6 months, 12 months, 18 months, and 24 months follow-up.
- IPF-T evaluated at 30 days, 90 days, 6 months, 12 months, 18 months, and 24 months.
- Secondary Patency evaluated through 30 days, 90 days, 6 months, 12 months, 18 months, and 24 months.
- Acute Technical Success.
- Acute Procedure Success (Anatomic and Clinical Success).

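### The 6-month TLPP test is specified only in implanted subjects; a subject who ends with no COVERA stent enters no specified effectiveness analysis, and a supportive ITT test would be a cheap improvement

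*Combined protocol and SAP*

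**What the plan says.** Section 2.2 defines ITT by introduction of the delivery system after eligibility is met and PTA has succeeded. It addresses failed delivery directly: "Subjects who do not receive the study device, but into which the COVERA™ Vascular Covered Stent System was introduced, will be included in the ITT". MITT is narrower: "any subjects in the ITT population who are treated with the COVERA™ Vascular Covered Stent (following PTA").

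The populations are then assigned to analyses:

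- Primary analyses: "All analyses including the primary analyses will be primarily based on the MITT population".
- ITT: "Key safety analysis will be performed based on ITT population as well".
- Per-protocol, which is a subset of MITT: "PP analyses may also be performed for the primary endpoints".

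Section 2.6.2 tests the study device treatment group against 40% and names no second population: "A one sided p-value will be derived based on an exact binomial test". Section 2.7 summarises the secondary endpoints, Acute Technical Success among them, in MITT as well. The Enrollment entry of the Protocol Summary counts implanted subjects: "Enrollment will continue until a total of one-hundred nine (109) subjects are treated with the COVERA™ Vascular Covered Stent". A subject who is not implanted therefore does not use one of the 109 places.

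**The concern.** The stated objective is the effectiveness of the device for treating stenosis at the graft-vein anastomosis. If the system enters the patient and no stent is placed, many readers would call that attempt a failure of the treatment. The loss from ITT to MITT happens after the attempt has begun, and a single-arm comparison with a fixed goal has no control group in which a similar loss could offset it.

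The other analyses in the plan do not cover the gap. Per-protocol can only remove subjects from MITT. The survival, worst-case and tipping-point analyses in section 2.4 deal with endpoints missing through withdrawal, investigator decision, loss to follow-up or death; a non-implanted subject lies outside MITT and is not a missing value within it.

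At stake is whether a narrow pass against 40% would depend on leaving those subjects out, with no planned TLPP result to show it either way.

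**Working it through.** **Inputs.** From section 2.5: goal 40%, assumed rate 55%, one-sided alpha 0.05, 109 treated, 93 evaluable after 15% attrition, 90% power. From section 2.6.2: exact binomial test. The number f of introduced-but-not-implanted subjects is not given in the documents, so a range is assumed.

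**1. The plan's own figure.** Normal approximation:

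n = [(1.645·√(0.40·0.60) + 1.282·√(0.55·0.45)) / 0.15]² = 92.6, so 93, with power 90.1%.

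Attrition: 109 × 0.85 = 92.65. The stated figures reproduce. With the exact test at n=93, the smallest pass is 46 successes: P(X≥46 | 93, 0.40) = 0.0404, and power at 55% is 88.0%. The sample size is not in dispute.

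**2. Scoring the f subjects as failures.** The s successes stay the same and the denominator becomes 93+f, so p = P(X≥s | 93+f, 0.40).

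| MITT result | MITT p | Largest f that still passes | First f that fails |
|---|---|---|---|
| 46/93 | 0.0404 | f=1: 46/94, p=0.0491 | f=2: 46/95, p=0.0591 |
| 48/93 | 0.0153 | f=5: 48/98, p=0.0444 | f=6: 48/99, p=0.0535 |
| 51/93 (0.55 × 93 = 51.15) | 0.0027 | f=12: 51/105, p=0.0461 | f=13: 51/106, p=0.0551 |

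With f of 0 or 1, every result that passes in MITT also passes in ITT.

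**3. Chance that the MITT test passes when the ITT rate is exactly 40%.** With the f subjects scored as failures, the rate among implanted subjects is 0.40·(N+f)/N, and the pass probability is P(X≥46 | 93, that rate). N can be taken as the 109 implanted subjects, beside whom failed deliveries arise, or as the 93 evaluable.

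| f | Implanted rate, N=109 | Pass probability | Implanted rate, N=93 | Pass probability |
|---|---|---|---|---|
| 0 | 0.4000 | 4.0% | 0.4000 | 4.0% |
| 2 | 0.4073 | 5.5% | 0.4086 | 5.8% |
| 5 | 0.4183 | 8.3% | 0.4215 | 9.3% |
| 6 | 0.4220 | 9.5% | 0.4258 | 10.8% |

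The 4.0% baseline lies below 5% because the exact test is discrete.

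**4. What the ITT test would cost in power.** At a true implanted rate of 55%, the cut-offs are 47/95, 48/98 and 49/99 for f = 2, 5 and 6. The power of the ITT test is P(X≥cut-off | 93, 0.55) = 83.4%, 77.7% and 71.0%, against 88.0% in MITT.

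**The case against.** The choice of population is pre-specified and consistent: the test, the sample size and the enrollment rule all refer to treated subjects. The documents do not say whether the literature rates behind the 40% goal describe implanted or attempted subjects. If they describe implanted subjects, MITT is the like-for-like comparison. Subjects who reach ITT have already had successful PTA, so a lesion left without a stent may stay patent. The supplied text does not define TLPP in a way that settles how such a subject would be scored, so scoring all of them as failures is a convention and not an observation. Failed deliveries may also be rare. All of this stands. It is why MITT should remain primary and why the weight is limited.

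Four stronger readings are tempting, and the documents do not support them.

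- A reader might infer that a failed delivery can never count against effectiveness. A failed first attempt followed by implantation stays in MITT and can count; the gap concerns only subjects who end with no study stent.
- A reader might infer that the MITT rate is always biased upward. That follows only if non-implanted subjects are regarded as failures.
- A reader might take the power differences in step 4 (about 5, 10 and 17 points), or the 8%, 16% and 24% obtained at an implanted rate of 50%, as chances of a false success. In those scenarios the true ITT rate is 0.50 or 0.55 × 93/(93+f), which lies between 47.0% and 53.8%. An MITT pass is then correct in either population, and the figures measure power lost by the ITT test.
- A reader might infer that the exclusion would be invisible. The ITT safety analysis should give an ITT count beside the MITT count, from which the number left out could be worked out. That still leaves the reader to construct the TLPP result, and the scoring rule, after the data are known.

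The word primarily in section 2.2 leaves room for other analyses, but no ITT analysis of effectiveness is specified.

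**Conclusion.** The point holds in limited form. No specified effectiveness analysis includes a subject into whom the system was introduced but who ends with no COVERA stent. If such subjects are regarded as treatment failures, the MITT rate overstates the effectiveness of attempted treatment, and a narrow pass could rest on their exclusion: two are enough at 46/93, six at 48/93 and thirteen at 51/93. On the same convention, with a true ITT rate of exactly 40%, the MITT test passes with probability about 5.5–5.8%, 8.3–9.3% and 9.5–10.8% for two, five and six such subjects, against 4.0% with none.

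These sizes rest on an assumed count, on 93 evaluable implanted subjects and on the failure convention. With none or one such subject, no decision changes. The severity is low to moderate: a cheap improvement, not a flaw in the primary decision rule.

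**What to change.** Keep MITT as the primary population. Add to sections 2.2 and 2.6.2 wording such as: *As a supportive analysis, the exact binomial test of 6-month TLPP against 40% and its exact one-sided 95% lower limit will also be computed in the ITT population, counting each subject into whom the system was introduced but who received no COVERA stent as a TLPP failure. This scoring is a conservative convention. The number of such subjects, and whether the ITT and MITT conclusions agree, will be reported beside the primary result.*

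The cost is a short addition to the SAP and one table row. Because failure is assigned at the procedure, no further follow-up of these subjects is needed, and the sample size, alpha and primary test are unchanged. The downside is a supportive rate slightly below the MITT rate: with two such subjects, 51/95 = 53.7% against 51/93 = 54.8%.

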2.3 Assessment of the Poolability of Investigational Sites

The sites will be tested for potential differences in the primary endpoints. Sites with fewer than 10 treated subjects may be combined for this purpose. The sites with less than 10 subjects will be sorted by site number and pooled by order to form one or more combined site(s) with at least 10 treated subjects. A logistic regression analysis will be performed with sites as a fixed effect. If the p-value associated with the site effect is <0.15 , it will be considered as evidence of statistical significance. Additional analyses

will be performed to explore the differences between sites to assess their potential causes and whether or not they are clinically meaningful.

2.4 Handling of Missing Data

Study endpoints may be missing due to withdrawal of consent, Investigator's decision, LTF and subject death. It is important to minimize missing data by all means and always record the reason for missing. Missing data will be handled as described subsequently.

As a sensitivity analysis, the primary effectiveness and safety endpoints will also be analyzed using survival analysis techniques. In survival analyses, unobserved endpoints are a standard part of the analysis; they are known as "censored observations". As long as the censoring is unrelated to the treatment, this method of handling missing endpoints produces unbiased estimates of the freedom-from-event rates. For both primary endpoints, the reason for the censoring of all subjects with missing endpoints will be reported. If there is any indication that the censoring is related to the study intervention, a worst-case analysis may be performed for each primary endpoint, in addition to the standard analysis. In a worst-case analysis, an event will be assumed to have occurred at the time the subject was censored for all such subjects.

In addition, regardless of whether missing data are related to the study intervention, a tipping-point analysis will also be performed, in which assumptions about missing data are varied from worst-case to best-case to examine at what point the missing data would alter the results of the analysis.

2.5 Sample Size Estimation

The sample size calculation assumes the following:

- 1) Primary Effectiveness Endpoint – TLPP at 6 months performance goal.
 - Assumptions:
 - The COVERA™ Vascular Covered Stent composite freedom from event rate is estimated at 55%;
 - The PG is set at 40%;
 - Attrition (drop-out) rate (by 6 months) = 15%;
 - The Type 1 error, $\alpha = 0.05$ (one-sided); and
 - The Type 2 error, $\beta = 0.10$ (Power = $1 - \beta = 90\%$).
 - Sample Size:
 - 109 treated subjects [93 evaluable] will give 90% power with one-sided type I error =0.05.
- 2) Primary Safety Endpoint – Safety at 30 days:
 - Assumptions:
 - The primary safety rate through 30 days in the study device treated subjects is 98%;
 - The PG is set at 88%;

- Attrition rate (by day 30) = 5%; and
- The Type 1 error, $\alpha = 0.05$ (one-sided).
- Sample Size:
 - 109 treated subjects [104 evaluable] will give 99% power with one-sided type I error =0.05.

Hence, the sample size of 109 subjects will provide approximately $(99\%)*(90\%)=89\%$ power for the both primary effectiveness and primary safety endpoint.

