2.6.4 Primary Safety Endpoint Hypothesis Test

The primary safety endpoint is safety through 30 days. Objective: To assess if the 30-day primary safety rate for the study device is greater than the safety PG:

H_0 : The proportion of subjects in the study device treatment group (P_{CS}) free from safety events in the primary safety endpoint is less than or equal to the safety PG of 88%.

H_1 : The proportion of subjects in the study device treatment group (P_{CS}) free from safety events in the primary safety endpoint is greater than the safety PG of 88%.

That is:

H_0 : $P_{CS} \leq 88\%$,

H_1 : $P_{CS} > 88\%$,

Rejection of the null hypothesis will signify that the 30 day safety of the COVERA™ Vascular Covered Stent is greater than the safety PG of 88%.

A one sided p-value will be derived based on an exact binomial test. The study device will be considered to have achieved the primary safety objective if the one-sided p-value is less than 0.05. Or equivalently, the lower limit of the one-sided 95% confidence limit based on exact method is greater than 88%.

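### Section 2.5 states 90% power for effectiveness, but the exact binomial test in section 2.6.2 has 88.0% at the planned 93 evaluable subjects; joint power is about 88%, not 89%

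*Combined protocol and SAP*

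**What the plan says.** Section 2.5 (Sample Size Estimation) sizes the study on 6-month target lesion primary patency (TLPP). It assumes a rate of 55% against a performance goal of 40%, one-sided alpha of 0.05, beta of 0.10 and 15% attrition by 6 months. It concludes: "109 treated subjects [93 evaluable] will give 90% power with one-sided type I error =0.05". No test or power formula is named.

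For 30-day safety, the same section assumes 98% against a goal of 88% with 5% attrition, and states 99% power at 104 evaluable. It then multiplies the two powers: "Hence, the sample size of 109 subjects will provide approximately" 99% × 90% = 89% for both endpoints together.

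Section 2.6.2 fixes the effectiveness test: "A one sided p-value will be derived based on an exact binomial test". Success requires a one-sided p-value below 0.05, or equivalently an exact one-sided 95% lower limit above 40%. Section 2.6.4 sets the same kind of rule for safety, with a limit of 88%.

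**The concern.** Power belongs to a particular test. An exact binomial test rejects only from a whole number of successes upward, so its attained type I error is usually below the nominal 0.05 and its power is usually below what a smooth normal formula gives. A power figure from such a formula can therefore overstate the power of the test that will be used. Section 2.5 is where a reader learns the chance of success on the primary endpoints, so its figures should belong to the tests in sections 2.6.2 and 2.6.4. What is at stake is the accuracy of that stated chance; the validity of the test is not in question.

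**Working it through.** **Inputs.** From section 2.5: p0 = 0.40, p1 = 0.55, one-sided alpha 0.05, 90% power, 15% attrition, 93 evaluable, 109 treated; for safety 0.88, 0.98 and 104 evaluable. From sections 2.6.2 and 2.6.4: exact binomial test, success if p < 0.05.

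**1. Reproducing the plan's figures.** One-sample normal approximation, with null variance for alpha and alternative variance for power:

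n = [(z₀.₉₅ √(p0(1−p0)) + z₀.₉₀ √(p1(1−p1))) / (p1−p0)]²
= [(1.645 × √0.24 + 1.282 × √0.2475) / 0.15]²
= [(0.806 + 0.638) / 0.15]² = 92.59, rounded up to 93.

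- Power at 93: Φ[(0.15 × √93 − 1.645 × √0.24) / √0.2475] = Φ(1.288) = 90.1%.
- Treated: 92.59 / 0.85 = 108.93, rounded up to 109.

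The stated 93, 90% and 109 are all recovered.

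**2. The exact test at 93 evaluable.**

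| Successes | One-sided p at 40% | Exact 95% lower limit | Result |
|---|---|---|---|
| 45/93 (48.4%) | 0.0621 | 39.5% | fails |
| 46/93 (49.5%) | 0.0404 | 40.5% | passes |

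The cut-off is 46, and attained type I error is 0.040. Power is P(X ≥ 46 | n = 93, p = 0.55) = 0.8804. A cut-off of 45 would give 91.7%, but section 2.6.2 does not allow it because p is above 0.05. No permitted cut-off at 93 reaches 90%.

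**3. Sensitivity to the evaluable count.** Exact power is saw-toothed:

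| Evaluable | 91 | 92 | 93 | 94 | 95 |
|---|---|---|---|---|---|
| Cut-off | 45 | 46 | 46 | 46 | 47 |
| Power at 55% | 87.9% | 85.7% | 88.0% | 90.0% | 88.2% |

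The expected count is 109 × 0.85 = 92.65. If the evaluable count is taken as Binomial(109, 0.85), which is an assumption, average power is 87.8%. Among the sizes computed (86 to 111), power stays at or above 90% only from 102 evaluable, which is 102 / 0.85 = 120 treated at the planned attrition.

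**4. Safety at 104 evaluable.** The cut-off is 98: P(X ≥ 98 | 0.88) = 0.0274. Power is P(X ≥ 98 | 0.98) = 0.9950, slightly above the stated 99%.

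**5. Joint power.** By the plan's product rule, 0.8804 × 0.9950 = 0.876. Without assuming independence, joint power is at least 0.8804 + 0.9950 − 1 = 0.875 and at most 0.880, so 89% is not reached under any dependence between the endpoints.

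**The case against.** The strongest reply is that the gap is smaller than the precision of the planning inputs. The 55% is an estimate; at a true rate of 55.5% the same cut-off gives 89.9% power, and at 56% it gives 91.5%. One more evaluable subject gives 90.0%. Sizing with a closed-form formula and analysing with an exact test is common, the stated 90% does reproduce, and the joint figure is labelled approximate. Section 2.5 also names no method, so the normal approximation is an inference. The same formula would give 99.97% for safety, so the stated 99% does not point to one method for both endpoints.

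Much of this stands. The shortfall is small, no sentence in section 2.5 directly contradicts section 2.6.2, and the source of the 90% cannot be proved. It does not make the 90% correct. Power is quoted at the stated 55% and 93 evaluable, and there the specified test has 88.0% whichever formula was used. Nor is 93 an unlucky count: every evaluable number from 86 to 93 gives less than 90%, and the average over attrition is 87.8%.

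**Conclusion.** The concern holds and is minor. Under the test the SAP specifies, effectiveness power at 93 evaluable is 88.0% against the stated 90%, a shortfall of 2.0 points. The chance of missing the goal when the true rate is 55% is therefore about 12% and not 10%. Joint power is 87.6% against about 89%, a shortfall of 1.4 points. Stated safety power is not overstated.

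These results rest on the plan's own rates, alpha and evaluable counts; only the 87.8% average needs the added assumption of binomial attrition. The count of 109 treated is consistent with the plan's inputs under the normal approximation, the type I error of the exact test is below 0.05, and no conclusion drawn from the trial would change.

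**What to change.** Keep 109 treated subjects and the exact test, and restate section 2.5 for that test, for example:

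> Power is calculated for the exact one-sided binomial test. With 93 evaluable subjects, effectiveness success requires at least 46 with TLPP through 6 months; attained one-sided type I error is about 0.04 and power is about 88% at an assumed rate of 55%. With 104 evaluable subjects, safety success requires at least 98 free from safety events; power is 99.5% at an assumed rate of 98%. Power for both endpoints is about 88%. Because the test is discrete, effectiveness power changes with the evaluable count (85.7% at 92, 90.0% at 94). The cut-offs apply to these counts only; the p < 0.05 rule applies at any count.

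The cost is corrected figures in one section and a stated power about 2 points less favourable. Sample size, test and follow-up are unchanged.
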